13.2.2 Overview of Treatment-emergent Adverse Events by Subgroups

Population: Safety Set

Target Phases: Core Phase, Core Phase and Extension Phase

Analysis items: - TEAEs, Related TEAEs, Serious TEAEs, Serious Related TEAEs, TEAEs by maximum severity (Grade 1, Grade 2, Grade 3, Grade 4, Grade 5, Grade ≥ 3), TEAEs of Special Interest (Thromboembolic events, Bleeding events (CTCAE Grades 3 and 4)), Related TEAEs of Special Interest, TEAEs leading to death

Contents: - Conduct a subgroup analysis for "[13.2.1 Overview of Treatment-emergent Adverse Events](#)". Subgroups are below:

- Sex (Male, Female)
- Age (<65 yrs, ≥ 65 yrs)

- Baseline platelet count ($\leq 15 \times 10^9 / L$, $> 15 \times 10^9 / L$)
- Use of concomitant ITP medications (Yes, No)
- Splenectomy status (Yes, No)
- Baseline creatinine clearance ($30 \leq - < 60 \text{ mL/min}$, $60 \leq - < 90 \text{ mL/min}$, $\geq 90 \text{ mL/min}$, Missing (if any))

Definitions: - The denominator to calculate the proportion is the number of subjects in each subgroup.

13.2.3 Treatment-emergent Adverse Events by SOC and PT

Population: Safety Set

Target Phases: Core Phase, Core Phase and Extension Phase

Analysis items: - TEAEs, Related TEAEs, Serious TEAEs, TEAEs leading to death

Contents: - The number and proportion of subjects with the Analysis items are calculated.
- The number and proportion of subjects in case of the other Analysis items are calculated by SOC and PT.

Definitions: - The denominator to calculate the proportion is the target population.

13.2.4 Treatment-emergent Adverse Events of Special Interest by AESI Category and PT

Population: Safety Set

Target Phases: Core Phase, Core Phase and Extension Phase

Analysis items: - TEAEs of Special Interest (Thromboembolic events, Bleeding events (CTCAE Grades 3 and 4))

Contents: - The number and proportion of subjects with the Analysis items are calculated.
- The number and proportion of subjects in case of the other Analysis items are calculated by AESI Category and PT.

Definitions: - The denominator to calculate the proportion is the target population.

13.2.5 Treatment-emergent Adverse Events by SOC and PT by Subgroups

Population: Safety Set

Target Phases: Core Phase, Core Phase and Extension Phase

Analysis items: - TEAEs

Contents: - Conduct a subgroup analysis for “[13.2.3 Treatment-emergent Adverse Events by SOC and PT](#)”. Subgroups are below:

- Sex (Male, Female)
- Age (<65 yrs, ≥65 yrs)
- Baseline platelet count ($\leq 15 \times 10^9 / L$, $> 15 \times 10^9 / L$)
- Use of concomitant ITP medications (Yes, No)
- Splenectomy status (Yes, No)
- Baseline creatinine clearance ($30 \leq - < 60 \text{ mL/min}$, $60 \leq - < 90 \text{ mL/min}$, $\geq 90 \text{ mL/min}$, Missing (if any))

Definitions: - The denominator to calculate the proportion is the number of subjects in Subgroup.

13.2.6 Treatment-emergent Adverse Events by PT

Population: Safety Set

Target Phases: Core Phase, Core Phase and Extension Phase

Analysis items: - TEAEs

Contents: - The number and proportion of subjects with TEAEs are calculated by PT and ordered by decreasing frequency.

Definitions: - The denominator to calculate the proportion is the target population.

13.2.7 Treatment-emergent Adverse Events by SOC, PT and Maximum Severity

Population: Safety Set

Target Phases: Core Phase, Core Phase and Extension Phase

Analysis items: - TEAEs

Contents: - The number and proportion of subjects with the Analysis items are calculated by severity.
- The number and proportion of subjects with the Analysis items are calculated by SOC and PT and by severity.

Definitions: - Severity: Grade 1, Grade 2, Grade 3, Grade 4, Grade 5, \geq Grade 3
- The denominator to calculate the proportion is the target population.

13.2.8 Treatment-emergent Adverse Events by Time to Onset and by PT

Population: Safety Set

Target Phases: Core Phase, Core Phase and Extension Phase

Analysis items: - TEAEs

Contents: - The number and proportion of subjects with the Analysis items are calculated by Time to Onset and by PT.

Definitions: - Time to Onset (months) = (Date of onset of TEAE - Date of start of treatment in Core Phase + 1) / 30.4375

- Time to Onset (Category):
 - Core Phase: [<3 months, 3≤ - <6 months, ≥ 6 months]
 - Extension Phase: [<3 months, 3≤ - <6 months, 6≤ - <9 months, 9≤ - <12 months, 12≤ - <15 months, 15≤ - <18 months, ≥18 months]
- The denominator to calculate the proportion is the target population.

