### 2.2 Extension Phase

## 2.2.1 Primary Objective

In the Extension Phase, the primary objective is to evaluate the safety and tolerability of long-term therapy with avatrombopag in Japanese subjects with chronic ITP.

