- d: Visits scheduled on a weekly basis should occur within a +/- 2-day timeframe, except Day 5 this visit should occur within +/- 1 day and Day 8 this visit should occur within a +2-day window. Visits scheduled on an every 2-week basis should be within a +/- 3-day timeframe.
- e: At Visit 22 the inclusion/exclusion criteria for the Extension Phase should be reviewed to confirm subject eligibility for those subjects who are willing to enter the Extension Phase.
- f: The physical exam will be performed at Week 20 and Week 34.
- g: The Screening Visit and Day 1 Baseline Visit platelet count will be averaged to obtain the baseline platelet count value. The 2 samples must be obtained  $\geq$ 48 hours and  $\leq$ 2 weeks apart and the results must be available prior to enrollment. Therefore, an additional screening platelet count maybe required due to issues with scheduling.
- h: To be performed at Visit 30 during Follow-up only:
- i: The sparse PK sample will be obtained at Visits 4, 7, 8, 13, and 22 (EOT).
- j: At Visits 5 and 10, one blood sample will be obtained pre-dose (trough), one sample between 2 and 4 hours post-dose, and another sample between 6 and 8 hours post-dose. Therefore, subjects should be instructed to take the study drug at the clinic during this visit, after collection of the pre-dose PK sample. These visits should be scheduled on a subject's regular dosing day. Serial sampling may need to occur at a visit later than Visit 5 or Visit 10 if study drug has been held or the dosing regimen has changed in the previous week. This is to ensure that the subject has been on a stable dose for at least 1 week when serial samples are collected.
- k: The pregnancy test will be performed at Week 20 and Week 34.

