7.4 Safety Set (SAF)

The Core Phase Safety Set will include all subjects who receive at least 1 dose of study drug and have a post-dose safety assessment. The Extension Phase Safety Set will include all subjects who receive at least 1 dose of study drug in the Extension Phase and have a post-dose safety assessment in the Extension Phase. General Issues for Statistical Analysis.

8 General Issues for Statistical Analysis

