8.6 Visit Windows

No formal visit windowing will be conducted, except assign appropriate visit per study day for the records of the End of Study visit (VISIT 22). Only scheduled visit assessment will be used in

the by visit analyses. If multiple records are found within the visit window, the record closest to target date will be used for analysis purposes.

All assessments will be used when calculating cumulative and maximum duration of platelet response. The visit target date will be used to impute the missing visit date.

All assessments during scheduled and unscheduled visits will be listed in the data listing and presented in individual subject figures.

| Analysis Visit | Analysis Window Target | Analysis Window Beginning Timepoint | Analysis Window Ending Timepoint |
|--------------------|------------------------|-------------------------------------|----------------------------------|
| Baseline | 1 day | - | 1 day |
| Visit 3 (Day 5) | 5 days | 2 days | 6 days |
| Visit 4 (Day 8) | 8 days | 7 days | 11 days |
| Visit 5 (Week 2) | 14 days | 12 days | 17 days |
| Visit 6 (Week 3) | 21 days | 18 days | 24 days |
| Visit 7 (Week 4) | 28 days | 25 days | 35 days |
| Visit 8 (Week 6) | 42 days | 36 days | 49 days |
| Visit 9 (Week 8) | 56 days | 50 days | 63 days |
| Visit 10 (Week 10) | 70 days | 64 days | 77 days |
| Visit 11 (Week 12) | 84 days | 78 days | 91 days |
| Visit 12 (Week 14) | 98 days | 92 days | 105 days |
| Visit 13 (Week 16) | 112 days | 106 days | 119 days |
| Visit 14 (Week 18) | 126 days | 120 days | 129 days |
| Visit 15 (Week 19) | 133 days | 130 days | 136 days |
| Visit 16 (Week 20) | 140 days | 137 days | 143 days |
| Visit 17 (Week 21) | 147 days | 144 days | 150 days |
| Visit 18 (Week 22) | 154 days | 151 days | 157 days |
| Visit 19 (Week 23) | 161 days | 158 days | 164 days |
| Visit 20 (Week 24) | 168 days | 165 days | 171 days |
| Visit 21 (Week 25) | 175 days | 172 days | 178 days |
| Visit 22 (Week 26) | 182 days | 179 days | 299 days |

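### SAP 13.2.8 gives every onset interval the same full Safety Set denominator, so late-interval percentages understate interval-specific incidence once subjects have left or not yet reached the interval

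*SAP*

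**What the plan says.** SAP 13.2.8 tabulates TEAEs by preferred term and onset interval. The analysis set is given as "Population: Safety Set", and the rule for every percentage is "The denominator to calculate the proportion is the target population".

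Onset is measured from the start of Core treatment: "Time to Onset (months) = (Date of onset of TEAE - Date of start of treatment in Core Phase + 1) / 30.4375". The Core intervals are "Core Phase: [<3 months, 3≤ - <6 months, ≥ 6 months". The longer list, headed Extension Phase, has 3-month steps up to 18 months and then one open interval.

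SAP 7.4 defines membership of the Core set by early events only: "The Core Phase Safety Set will include all subjects who receive at least 1 dose of study drug and have a post-dose safety assessment". It defines a separate Extension Safety Set. SAP 13.2.8 does not say which of the two serves the combined Core and Extension table. The section plans no count at risk per interval and no rate per unit of exposure.

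**The concern.** A table by time to onset invites reading across the columns to see whether events become rarer or more frequent with longer treatment. That comparison needs each column to be divided by the subjects who could have had an event in it. Here the divisor is fixed while the number observed can shrink, for three documented reasons:

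- Subjects who terminate early are not replaced (Protocol 5.3).
- Entry to the Extension is optional (Protocol 4.3.4).
- The first analysis follows the last subject's Core completion, when the SAP expects some subjects to be ongoing in the Extension (SAP 5.4 and 9.2). Those who have not reached a late interval are still counted in it.

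A falling row of percentages could then be taken for falling risk when it reflects only fewer subjects observed. This bears on the Extension's primary objective, which is to "evaluate the safety and tolerability of long-term therapy with avatrombopag".

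**Working it through.** **Step 1: the plan's own day count.** 26 weeks × 7 = 182 days. This matches the target day in SAP 8.6: "Visit 22 (Week 26) | 182 days | 179 days | 299 days".

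**Step 2: where the last Core interval opens.** With the SAP's divisor, 6 × 30.4375 = 182.625 days.

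- Day 182: 182/30.4375 = 5.979 months, in the interval below 6 months.
- Day 183: 183/30.4375 = 6.012 months, the first day in the interval from 6 months.

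So the interval opens one day after the nominal end of the 26-week period.

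**Step 3: who can contribute to it.** Protocol Appendix A says "Visits scheduled on a weekly basis should occur within a +/- 2-day timeframe", so Visit 22 may fall as late as Day 182 + 2 = Day 184. Only Days 183 and 184 can therefore overlap the 26-week period on schedule. After that, only subjects who do not enter the Extension remain in the Core Phase (Protocol 4.1). They have up to 4 weeks of taper (Protocol 4.3.5; to about Day 210, or 6.90 months) and 4 weeks of follow-up (Protocol 4.3.6; to about Day 238, or 7.82 months). I assume that the Core table does not count events with onset after Extension entry.

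**Step 4: size of the denominator effect.** With x subjects having an onset in an interval, the table reports x/N. The incidence among those observed is x/n, where n is the number at risk. The ratio of the second to the first is N/n.

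N = 19 is the planned enrolment (SAP 4.2 says at least 19). The values of x and n are assumptions, because the documents state neither a dropout rate nor a rollover rate. For x = 2:

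| At risk (n) | Reported, 2/19 | At-risk figure, 2/n | Factor, 19/n |
|---|---|---|---|
| 19 | 10.5% | 10.5% | 1.00 |
| 17 | 10.5% | 11.8% | 1.12 |
| 10 | 10.5% | 20.0% | 1.90 |
| 7 | 10.5% | 28.6% | 2.71 |

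For the last Core interval with one event, the table reports 1/19 = 5.3%. If 8, 5, 3 or 2 subjects enter taper and follow-up, the at-risk figure is 12.5%, 20.0%, 33.3% or 50.0%.

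**Step 5: practice elsewhere in the SAP.** The abnormal-laboratory table (SAP 13.3.2) removes subjects discontinued before or at the visit. The by-visit response tables (SAP 11.3.6 to 11.3.8) use subjects with data at the visit. The time-to-onset table does neither.

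**The case against.** The fixed-denominator percentage is correctly defined: it is the share of the analysis set with onset in that interval. SAP 13.2.8 states its denominator openly and never calls the result a risk. This stands. The figure misleads only when columns are compared as risks, although a layout by interval encourages that comparison.

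A reader might infer that late percentages must fall, or that the long-term safety conclusion is biased. The documents do not support either. The effect is zero if everyone remains and has reached the interval, and no attrition figure is given. This is one descriptive table among several adverse event summaries, and no testing is planned (SAP 8.3.5). The listings in SAP Section 14 show each subject's events and exposure, so the counts can be rebuilt for a trial of this size. The first-analysis problem also eases at the final analysis. The exposure milestones in SAP 13.1 help less, because apart from 26 and 52 weeks they do not line up with the 3-month cut points.

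A reader might also infer that the last Core column lies wholly after treatment, or is empty. Neither follows: study drug may continue during taper, and a late Visit 22 can add two days. The column nearly isolates taper and follow-up already; what it lacks is a matching label and denominator.

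Finally, if the Extension Safety Set applies to the combined table, subjects who left during the Core Phase are already excluded and N is no longer 19. The denominator would still be fixed across later intervals, so the point remains with a different N.

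**Conclusion.** The point holds as a reporting weakness of minor weight. As a measure of interval-specific incidence, each late-interval percentage is too low by N/n whenever subjects have left or not yet reached the interval. Over the assumed range of 19 down to 7 at risk out of 19, the factor runs from 1.00 to 2.71. The true value cannot be fixed from the documents.

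The Core interval from 6 months is the clearest case. Apart from about two days of visit tolerance, subjects who rolled over cannot contribute to it, yet they remain in its denominator. That part needs no dropout assumption, only that some subjects roll over and that Core events stop at Extension entry.

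**What to change.** In SAP 13.2.8:

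- For each interval, take as denominator the subjects still under observation at its start, or report events per 100 subject-months. The rate suits the open last interval better, because follow-up within it varies in length.
- Print that n in each column header, and state the rule that ends a subject's observation.
- Name the Safety Set used for the combined Core and Extension table.
- Label the Core column from 6 months as taper/follow-up and give it its own n.
- If wanted, keep the present percentage alongside as the share of all treated subjects.

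The cost is minor programming from treatment and disposition dates already held. The drawback is noise: late intervals will rest on few subjects. Even 2/19 has an exact 95% interval of 1.3% to 33.1%, and with 8 at risk 2/8 = 25% has one of 3.2% to 65.1%. Showing n makes that imprecision visible.

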13.3 Laboratory Data

The list of laboratory parameters evaluated in this study is presented as below:

Table 1: List of Laboratory Test Items collected in Central Laboratory:

| Category | Items | Standard Units | Digit | Remarks |
|-------------|---------------------------------------|----------------|--------|---------------------------|
| Hematology | Hematocrit | fraction of 1 | 0.001 | Set based on current data |
| | Hemoglobin | g/L | 1 | |
| | Platelets | 10^9/L | 1 | |
| | Erythrocytes | 10^12/L | 0.01 | |
| | Basophils/Leukocytes | fraction of 1 | 0.001 | |
| | Eosinophils/Leukocytes | fraction of 1 | 0.001 | |
| | Lymphocytes/Leukocytes | fraction of 1 | 0.001 | |
| | Neutrophils/Leukocytes | fraction of 1 | 0.001 | |
| | Monocytes/Leukocytes | fraction of 1 | 0.001 | |
| | Leukocytes | fraction of 1 | 0.001 | |
| Chemistry | Alanine aminotransferase | ukat/L | 0.0001 | |
| | Aspartate aminotransferase | ukat/L | 0.0001 | |
| | Alkaline phosphatase (ALP) | ukat/L | 0.0001 | |
| | Direct bilirubin | umol/L | 0.0001 | |
| | Total bilirubin | umol/L | 0.0001 | |
| | Urea Nitrogen | mmol/L | 0.0001 | |
| | Sodium | mmol/L | 1 | |
| | Chloride | mmol/L | 1 | |
| | Bicarbonate | mmol/L | 0.1 | |
| | Creatinine | umol/L | 0.001 | |
| | Potassium | mmol/L | 0.1 | |
| | Glucose | mmol/L | 0.0001 | |
| | Calcium | mmol/L | 0.001 | |
| | Phosphate | mmol/L | 0.0001 | |
| Coagulation | Activated Partial Thromboplastin Time | s | 0.1 | |

| Category | Items | Standard Units | Digit | Remarks |
|----------|------------------------------------|----------------|-------|---------|
| | Prothrombin Intl. Normalized Ratio | | 0.01 | |
| | Prothrombin Times | s | 0.1 | |

Values under the lower limit of quantification (LLOQ) will be reported with inequality sign “<” and values over upper limit of quantification (ULOQ) will be reported with inequality sign “>”. Thus, the inequality signs should be removed and remaining values will be used in analyses.

13.3.1 Laboratory Parameters and Change from Baseline by Visit

Population: Safety Set

Target Phases: Core Phase, Extension Phase

Visits:

- Core Phase: Baseline, Visit 4 (Day 8), Visit 10 (Week 10), Visit 13 (Week 16), Visit 22 (Week 26), Follow-up (Week 1), Follow-up (Week 2), Follow-up (Week 3), Follow-up (Week 4)
- Extension Phase: E 1 (Month 1), E 2 (Month 2), E 4 (Month 4), E 5 (Month 5), E 7 (Month 7), E 8 (Month 8), E 10 (Month 10), E 11 (Month 11), E 13 (Month 13), E 14 (Month 14), E 16 (Month 16), E 17 (Month 17), E 19 (Month 19), E 20 (Month 20), E 22 (Month 22), E 23 (Month 23), E 24 (Month 24)

Analysis items:

- For the parameters to be analyzed refer to Table 1 in [13.3 Laboratory data](#)

Contents:

- Summary statistics of actual value and change from baseline of laboratory tests for each visit are calculated.

13.3.2 Laboratory Parameters with any Abnormal Measured Values by Visit

Population: Safety Set

Target Phases: Core Phase, Extension Phase

Visits:

- Core Phase: Baseline, Visit 4 (Day 8), Visit 10 (Week 10), Visit 13 (Week 16), Visit 22 (Week 26), Follow-up (Week 1), Follow-up (Week 2), Follow-up (Week 3), Follow-up (Week 4)
- Phase: E 1 (Month 1), E 2 (Month 2), E 4 (Month 4), E 5 (Month 5), E 7 (Month 7), E 8 (Month 8), E 10 (Month 10), E 11 (Month 11), E 13 (Month 13), E 14 (Month 14), E 16 (Month 16), E 17 (Month 17), E 19 (Month 19), E 20 (Month 20), E 22 (Month 22), E 23 (Month 23), E 24 (Month 24)

Analysis items:

- For the parameters to be analyzed refer to Table 1 in [13.3 Laboratory data](#)

Contents:

- The number and proportion of subjects with any abnormal measured values (High/Low) at each visit are calculated.

Definitions:

- The number of target population by each analysis visit is calculated.
- Abnormal measured values are defined as below:
 - High: actual value > upper limit of normal
 - Low: actual value < lower limit of normal
- The denominator to calculate proportion of subject with any abnormal measured values (High/Low) is the number of target population by each analysis visit (excluding discontinued subject before or at that visit).

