### **5.2** Exclusion Criteria

## **5.2.1** Primary Investigation Phase (Core Phase)

Subjects who meet any of the following criteria will not be eligible to participate in the study:

- 1. Subjects with known secondary immune thrombocytopenia (e.g., with known *Helicobacter pylori*-induced ITP, subjects infected with known human immunodeficiency virus [HIV] or HCV or subjects with known systemic lupus erythematosus).
- 2. Subjects with known inherited thrombocytopenia (e.g., MYH-9 disorders) or hereditary thrombophilic disorders (e.g., Factor V Leiden, antithrombin III deficiency).
- 3. History of myelodysplastic syndrome (MDS).
- 4. History of arterial or venous thrombosis.
- 5. Subjects with a history of significant cardiovascular disease (e.g., congestive heart failure [CHF] New York Heart Association Grade III/IV, arrhythmia known to increase the risk of thromboembolic events [e.g., atrial fibrillation], angina, coronary artery stent placement, angioplasty, coronary artery bypass grafting).
- 6. Subjects with a history of cirrhosis, portal hypertension, or chronic active hepatitis.
- 7. Subjects with concurrent malignant disease or receiving cytotoxic chemotherapy for a reason other than ITP treatment.
- 8. Use of immunoglobulins (IVIg and anti-D) or corticosteroid rescue therapy within 1 week of Day 1/Baseline.
- 9. Splenectomy or use of rituximab within 12 weeks of Day 1/Baseline.
- 10. Use of romiplostim or eltrombopag within 1 week of Day 1/Baseline.

- 11. Use of chronic corticosteroid treatment or azathioprine within 4 weeks of Day1/Baseline, unless receiving a stable dose for at least 4 weeks.
- 12. Use of mycophenolate mofetil, cyclosporin A, or danazol within 4 weeks of Day1/Baseline, unless receiving a stable dose for at least 12 weeks.
- 13. Use of cyclophosphamide or vinca alkaloid regimens within 4 weeks of Baseline Visit.
- 14. Currently receiving moderate or strong dual inhibitors/inducers of CYP2C9 and CYP3A4 (see Appendix D for examples).
- 15. Serum creatinine  $\geq 1.5 \times$  the upper limit of normal (ULN).
- 16. Serum bilirubin ≥2×ULN.
- 17. Alanine aminotransferase (ALT) or aspartate aminotransferase (AST)  $\geq 3 \times ULN$ .
- 18. Females who are pregnant (positive beta-human chorionic gonadotropin positive [β-hCG] test) or breastfeeding.
- 19. Known allergy to avatrombopag or any of its excipients.

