Clinically significant abnormal laboratory or other examination findings that are detected during the study or are present at the Screening Visit and significantly worsen during the study should be reported as AEs. The Investigator will exercise his or her medical and scientific judgment in deciding whether an abnormal laboratory finding, or other abnormal assessment is clinically significant. Clinically significant abnormal laboratory values occurring during the clinical study will be followed until repeat tests return to normal, stabilize, or are no longer clinically significant. Laboratory abnormalities are not considered AEs unless they are associated with clinical signs or symptoms or require medical intervention. Any abnormal test that is determined to be an error does not require reporting as an AE.

Clinically significant abnormal findings in physical examinations will be reported as AEs.

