# 10.2.3 Analysis of Safety

Evaluation of safety will be performed on the Safety Set. Safety data that will be evaluated include AEs, clinical laboratory results, and vital signs. All AEs will be coded using MedDRA. Adverse events will be coded to system organ class and preferred term using MedDRA. AEs will be presented with and without regard to causality based on the Investigator's judgment. The frequency of overall toxicity, categorized CTCAE criteria Grades 1 through 5, will be described. Treatment-emergent AEs (TEAEs) will be summarized by presenting the incidence of AEs. Descriptive summary statistics (mean plus standard deviation, median, and range) of the laboratory parameters, vital signs, and changes from baseline will be evaluated.

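### The laboratory abnormality table shows High/Low prevalence at each visit, so it cannot count subjects with a new or marked abnormality; add a baseline-to-worst shift table

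*SAP*

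**What the plan says.** SAP 13.3.2 sets out the only planned table of abnormal laboratory values: "The number and proportion of subjects with any abnormal measured values (High/Low) at each visit are calculated". The definitions are "High: actual value > upper limit of normal" and "Low: actual value < lower limit of normal". The denominator "is the number of target population by each analysis visit (excluding discontinued subject before or at that visit"), so it is not restricted to subjects who were normal at baseline. The Core Phase visit list starts "Core Phase: Baseline, Visit 4 (Day 8), Visit 10 (Week 10), Visit 13 (Week 16), Visit 22 (Week 26") and goes on to the follow-up weeks. The Extension Phase list starts at E1 and contains no Baseline entry.

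The other laboratory table, SAP 13.3.1, gives summary statistics of values and of change from baseline by visit. Individual values go to listing 16.2.8.1. SAP 8.6 limits by-visit analyses to scheduled assessments and reassigns End of Study (Visit 22) records to a visit by study day.

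Protocol 10.2.3 promises descriptive statistics and changes from baseline for laboratory parameters. Neither document plans a shift table, a count of treatment-emergent laboratory abnormalities or a graded laboratory table.

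**The concern.** Every subject receives open-label avatrombopag (Protocol 6.1), so the main internal evidence on laboratory safety is how each subject's results move from that subject's own baseline. Abnormal baselines are possible by design: Protocol 5.2.1, criteria 15 to 17, excludes creatinine only from 1.5×ULN, bilirubin only from 2×ULN and ALT/AST only from 3×ULN. A count of High values at a visit therefore combines subjects who arrived High with subjects who became High on drug.

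Nor does the count separate degrees of abnormality. An ALT unchanged from entry at 2.5×ULN and a new ALT of 10×ULN each add one to the same cell.

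For adverse events the SAP does use the pre-treatment state: its TEAE definition (SAP 13.2) requires an event to be new or worse than before treatment. Laboratory values get no equivalent, although safety is a secondary objective of the Core Phase and the primary objective of the Extension Phase (Protocol 2.1.2 and 2.2.1).

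**Working it through.** The plan states no figure on this point, so there is none to reproduce. Two things can be checked: what the by-visit counts can tell a reader, and which samples reach the table.

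**1. Bounds on newly High subjects**

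Inputs: N = 19 (SAP 6); four on-treatment Core laboratory visits, namely Day 8 and Weeks 10, 16 and 26 (SAP 13.3.2). The documents give no expected High counts, so those below are assumptions, as is assessment of all 19 subjects at every visit.

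Let k be the number High at Baseline and v the number High at each later visit.
- Newly High at one visit: from max(0, v − k) to min(v, N − k).
- Ever newly High over four visits: from max(0, v − k) to min(4v, N − k).

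| k at Baseline | v at each visit | New at one visit | Ever new over four visits |
|---|---|---|---|
| 0 | 1 | 1 to 1 | 1 to min(4, 19) = 4 |
| 1 | 1 | 0 to 1 | 0 to min(4, 18) = 4 |
| 2 | 2 | 0 to 2 | 0 to min(8, 17) = 8 |
| 4 | 4 | 0 to 4 | 0 to min(16, 15) = 15 |
| 6 | 6 | 0 to 6 | 0 to min(24, 13) = 13 |

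As percentages, 1/19 = 5.3% and 4/19 = 21.1%. The Baseline row does carry information: when it shows 0, a true count of zero newly High subjects is ruled out. When it shows 1 and every later row shows 1, the range is 0% to 21.1%, because the table does not say whether these are the same subject.

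**2. Where an early-termination sample goes**

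Protocol 5.3 asks for the EOT assessments when a subject leaves early, and Protocol 7.2.5 includes central-laboratory blood among them. Under SAP 8.6 such a record takes its visit from the study day. Before the Visit 22 window opens on day 179, the windows that belong to tabulated laboratory visits are:
- Visit 4, days 7 to 11: 5 days
- Visit 10, days 64 to 77: 14 days
- Visit 13, days 106 to 119: 14 days

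These total 33 of the 177 days from day 2 to day 178. The other 177 − 33 = 144 days (144/177 = 81.4%) fall in windows of visits that 13.3.1 and 13.3.2 do not list. A sample on day 55, for example, maps to Visit 9. Where the sample does map to a listed visit, the 13.3.2 denominator still leaves out a subject who discontinued before or at it. The 81.4% is a share of calendar days; it does not estimate how many samples would be lost.

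**The case against.** The case against has four parts, and much of it stands.

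*Baseline is in the table.* A reader might infer that the plan ignores baseline status. That is too strong for the Core Phase, where baseline prevalence is printed; what is missing is the within-subject link. The Extension Phase list lacks even the prevalence.

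*Other outputs would show a marked value.* A reader might also infer that a large rise could go unseen. The documents do not support that. SAP 13.3.1, with the statistics in SAP 8.3.1, prints the minimum and maximum of both value and change, so an extreme result at a listed visit would appear. Listing 16.2.8.1 allows new cases to be counted by hand in about 19 subjects. Two limits remain: a maximum does not say how many subjects worsened, and a hand count leaves the rule for new or marked to be chosen after the data are seen. In addition, SAP 8.3.3 defines change as value divided by baseline minus 1. A rise from 0.2 to 1.2×ULN and one from 1.5 to 9×ULN then both give 5.0.

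*Adverse event reporting covers it.* Protocol 9.1 requires clinically significant findings, including those present at screening that significantly worsen, to be reported as AEs. These would be graded and tabulated. The same section also says: "Laboratory abnormalities are not considered AEs unless they are associated with clinical signs or symptoms or require medical intervention". The two rules pull apart for an asymptomatic, untreated rise, so this backstop is real but uncertain.

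*The protocol is not breached.* The sentence "The frequency of overall toxicity, categorized CTCAE criteria Grades 1 through 5, will be described" in Protocol 10.2.3 might be read as an unmet promise to grade laboratory values. It stands among the AE sentences, and SAP 13.2.1 and 13.2.7 fulfil it. The SAP delivers what the protocol promises for laboratory data and adds the High/Low counts.

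**Conclusion.** The point holds as a minor safety-reporting gap. SAP 13.3.2 reports prevalence by visit. It cannot give the number of subjects with a new abnormality, the number with a marked one, or the number ever abnormal after baseline. In the simplest illustration (one High in the Baseline row and in every on-treatment row), the number newly High is anywhere from 0 to 4 of 19; it narrows to 1 to 4 if the Baseline row shows none. These ranges rest on assumed counts and complete assessment, and they describe 13.3.2 read alone. The full set of laboratory outputs would let a careful reader recover most of the information by hand. Early-termination values can be missing from both by-visit tables, although the listing should still hold them. The primary endpoint, alpha and sample size are not affected.

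**What to change.** Add to SAP 13.3.2, for each phase, a per-subject shift table from Core baseline category to worst post-baseline category, with the number and percentage of subjects who have a treatment-emergent abnormality. Specify that:
- worst post-baseline uses all scheduled, unscheduled and early-termination central-laboratory values;
- creatinine, bilirubin and ALT/AST are classified by CTCAE v5.0 grade, which Protocol 9.1.1.1 already uses for AEs, or by several multiples of ULN (one cut-off per test would leave moderate and extreme rises in the same category);
- the other tests use Low/Normal/High, with worst taken separately in each direction;
- treatment-emergent means not abnormal in that direction at baseline or, for graded tests, a higher category than at baseline.

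Keep the by-visit table as support. The cost is SAP wording before the Core Phase database lock and a little programming on data already collected.
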